Daily telephone or email follow-up: research personnel will contact participants by phone on a daily basis for 7 days post-randomization, and at 14 (+/- 3) and 30 days (+/- 3). They will conduct a structured interview to ascertain potential symptoms of COVID-19 (the primary outcome), adherence to and potential adverse effects of the study drug, and extent of ongoing exposure to the index case. Alternatively, if preferred by the participant, the participant will be able to submit answers to the daily symptomatic questionnaire via secure web-based questionnaire to support remote administration and immediate data capture. Participants with symptoms or signs of COVID-19 will be referred to the study physician, who will contact the participant and determine if he/she meets PUI criteria. The study physician will refer PUIs for confirmatory COVID-19 testing at NYP/CUIMC/WCMC.

Psychosocial Questionnaire at Day7: Resources for mental health and wellness are provided at the end of the psychosocial questionnaire for all participants, as well as instructions for seeking medical attention if participants experience significant distress or feel unsafe.

Participants who score in the severe or extremely severe range on the depression subscale, express passive or active suicidal ideation, or express thoughts of self-harm will be informed of mental health support hotlines, advised to seek care from a mental health professional, and encouraged to contact emergency services if they feel unsafe. For such participants who respond to the questionnaire online or by paper, an attempt will be made to contact them at the time the questionnaire is viewed to provide the information above.

Active surveillance of healthcare utilization: the research personnel will monitor study participants to determine if any participants present to the outpatient clinic or to the ED, and/or if they require hospitalization.

Extended follow-up of symptomatic participants: participants who develop COVID-19 symptoms will continue to be followed-up by daily telephone calls until 3 days following resolution of

symptoms in order to measure the duration of symptom (secondary endpoint).

Statistics

We plan a phase 2 study at NYP/CUIMC/WCMC, with the phase 2 as an internal pilot for a potential phase 3 study, which would be conducted across all NYP sites.

Population: Household contacts of COVID-19 cases with high-risk COVID-19 exposures

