The primary analysis will be comparing the rates of symptomatic, lab-confirmed COVID-19 in all randomized participants using one-sided Fisher's exact test. Intent-to-treat analysis will be used. Secondary endpoints include duration of COVID-19 symptoms without confirmatory test, hospitalization for COVID-19, requiring mechanical ventilation, and mortality. Statistical analysis of the secondary endpoints will be intent-to-treat, using Mann-Whitney test for numerical outcomes and Fisher's test for categorical outcomes. Adverse events and serious adverse events will be compared using Fisher's exact test. Interim analysis will be performed to monitor for futility using a Bayesian criterion. Specifically, an early stopping consideration will be invoked if it is unlikely that poor outcome of hPEP is lower than that of placebo; i.e., its posterior probability is smaller than alpha. The value of alpha will be determined before the first interim analysis.

Go and no-go decision and power consideration

We will plan to move forward to the phase 3 trial if at the end of the pilot phase, the primary analysis has a one-sided p-value less than 0.10. Assuming the placebo rate of COVID-19 outcome is 10.5%, the proposed sample size in the internal pilot will result in an 80% probability of moving forward if the study drug reduces risk by 30% (i.e., from 10.5% to 7.3%).

In addition, the pilot data will be used to re-estimate the sample size in the phase 3 trial, and will be used in the final analysis using adjusted analysis using weighted statistics so as to preserve the overall type I error. Details of sample size re-estimation will be determined before the pilot trial data is unblinded.

3. Study Procedures

a. Procedures

- i. Questionnaires: questionnaires will be performed by telephone by trained research assistants or via web-based questionnaire to support remote administration and immediate data capture.
 1. Screening questionnaire (first call): inclusion and exclusion criteria
 2. Medical history questionnaire (first call): additional questions regarding medications used, number of persons in household
 3. Follow-up questionnaires
 - a. Symptoms (respiratory, non-respiratory)
 - b. Trial medicine adherence
 - c. Psychosocial Behavior (Day7 only)
- ii. Active surveillance for health care utilization and COVID-19 testing at NYP/CUIMC
 1. Participants will be referred for clinical COVID-19 testing if deemed PUI by the study investigator(s)

b. Study Drugs

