e. Protections Against Risks:

- i. In addition to strict exclusion criteria, we will monitor participants for signs/symptoms of potential adverse effects of the study drug by daily follow-up for 7 days. On Day 7, a specific interview concerning acute side-effects of the study medication will be conducted. If any adverse drug effects are suspected based upon symptomatic report, the study physician will determine whether the symptoms are attributable to the study drug. Beyond the two-week period of initial follow-up, we will encourage all participants to reach out to the study coordinator for palpitations, dyspnea on exertion, or visual disturbances occurring up to 30 days after completion of participation. Serious adverse events (SAEs) will be recorded for the full duration of subject participation, however only adverse events of special interest will be recorded upon the Day 7 acute side-effect interview.
- ii. To mitigate risks of COVID-19 among participants, all participants will receive counseling and information regarding current CDC guidelines for exposed household contacts of COVID-19 patients (e.g., decontamination of surfaces, avoidance of unprotected contacts with the index case).

f. Potential Benefits: if the study drug is effective, those randomized to the study drug may benefit from improved COVID-19 outcomes. If benefit is demonstrated, participants randomized to the control arm will have the opportunity to obtain the study drug after study completion. The societal benefits are potentially large.

g. Alternatives: non-participation. Data Safety and Monitoring Plan: A local Data and Safety Monitoring Committee (DSMC) has been established, with [name] (rheumatology) as Chairman of the committee. In addition, the committee will consist of two other members, a pharmacist (TBD) and a statistician ([name]). The DSMC will meet to review all safety data from the patients after the first 100 randomized patients completing their 2-week follow-up, and every 400 randomized patients thereafter. The unblinded statistician will prepare the data for DSMC's review. Each meeting will consist of an open session that includes the study investigators, and a closed session with only the unblinded statistician and the DSMC members.

References

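### The planned between-arm comparison of adverse events has no matching dataset, because the recording rule for non-serious events covers only an unlisted special-interest set at day 7

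*Combined protocol and SAP*

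**What the plan says.** Four places in the combined protocol and SAP bear on this.

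- **Section 2, Follow up (daily telephone or email follow-up).** Staff contact participants on each of the first 7 days after randomization and again at days 14 and 30, each with a 3-day window. The structured interview covers "adherence to and potential adverse effects of the study drug".
- **Section 2, Additional notes on statistical design and analysis.** "Adverse events and serious adverse events will be compared using Fisher's exact test". Two categories are named, and the first carries no qualifier.
- **Section 3, item e, Protections Against Risks.** Under this item, "we will monitor participants for signs/symptoms of potential adverse effects of the study drug by daily follow-up for 7 days". The recording rule follows: "Serious adverse events (SAEs) will be recorded for the full duration of subject participation", but "only adverse events of special interest will be recorded upon the Day 7 acute side-effect interview".
- **Section 3, item g.** The DSMC reviews all safety data once the first 100 randomized participants have completed two weeks, and then after every further 400.

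The follow-up questionnaires listed in section 3, item a, cover respiratory and non-respiratory symptoms, adherence and, at day 7, psychosocial behavior. No adverse-event item is listed.

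**The concern.** The plan asks about harms widely, promises to analyze them without restriction, and records them narrowly. The recording rule sets full-duration capture of serious events against limited capture of the others, so it reads as a deliberate restriction. Staff who follow it would hear about a non-serious event on day 3 or day 14 and have no instruction to enter it as an adverse event.

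Participants are asymptomatic contacts taking a prophylactic, so tolerability carries real weight in judging benefit against risk. The same item of section 3 asks participants to report palpitations, exertional dyspnea or visual disturbance after the two-week period. The protocol thus treats some late non-serious events as worth knowing about, yet gives no rule for recording them. A DSMC told that it sees all safety data could take a restricted table for a complete one.

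**Working it through.** The point is textual. The plan gives no adverse event rate and no power figure for safety. Its only power figure, 80%, belongs to the primary efficacy analysis and does not bear on this.

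**Step 1: set elicitation, recording and analysis side by side.**

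| Type of event | Asked about | Stated recording rule | In the planned comparison |
|---|---|---|---|
| Serious | Every contact | Full duration of participation | Yes |
| Non-serious, special interest, at the day 7 interview | Yes | Yes, but the set is not listed | Yes |
| Non-serious, special interest, at day 14 or 30 | Yes | None | Yes |
| Non-serious, any other, at any contact | Yes | None | Yes |

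The last two rows are the gap: the comparison includes them, but no recording rule supplies them. There are 7 + 2 = 9 scheduled contacts per participant that ask about adverse effects. The recording rule for non-serious events names 1 of them.

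**Step 2: try the more favorable reading.** Suppose the day-7 sentence describes only that interview and other contacts feed the safety data separately. The documents would then need to say which forms do so. The interview description says what is asked, not what is kept as an adverse event. The questionnaire list includes non-respiratory symptoms, so some relevant answers may be stored, but nothing says they are coded or analyzed as adverse events. Under either reading the source of the adverse event comparison has to be stated.

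**Step 3: what could be at stake (illustration on assumed rates).** Let a fraction *c* of participants with an adverse event have it recorded, equal in both arms. Recorded rates are c·p₁ and c·p₂, so the risk ratio is unchanged and the absolute difference shrinks by *c*. With n = 800 per arm, two-sided 5% and the normal approximation:

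power = Φ[(d − 1.96·s₀)/s₁]

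where d is the difference in recorded rates, s₀ its pooled standard error and s₁ its unpooled standard error. For true rates of 10% and 5% with c = 0.5, the recorded rates are 5% and 2.5%:

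- s₀ = √(0.0375 × 0.9625 × 2/800) = 0.00950
- s₁ = √[(0.05 × 0.95 + 0.025 × 0.975)/800] = 0.00948
- power = Φ[(0.025 − 1.96 × 0.00950)/0.00948] = Φ(0.67) = 0.75

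| Assumed true rates | c = 1 | c = 0.75 | c = 0.5 | c = 0.25 |
|---|---|---|---|---|
| 10% v 5% | 0.97 | 0.90 | 0.75 | 0.45 |
| 8% v 5% | 0.68 | 0.55 | 0.39 | 0.22 |
| 4% v 2% | 0.65 | 0.53 | 0.38 | 0.21 |

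The rates, the values of *c* and the 5% level are all assumptions; the documents set no level for safety tests. The table shows only that restricted recording weakens a comparison by an amount that depends on *c*, and the plan gives no means of estimating *c*.

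**The case against.** The strongest defense is that this is intended selective collection. Section 1 describes the drug's safety profile as well established. The course lasts 5 days, so a day-7 interview falls after the whole dosing period. Serious events are captured throughout, and participants are invited to report three named symptoms later. If the special-interest list includes the common tolerability effects, little would be missed.

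Much of this is fair, and selective collection can be legitimate. It would still require a listed set and an analysis limited to that set, and the plan has neither.

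A reader might also draw stronger conclusions, which the documents do not support:

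- **That the safety comparison is impossible.** Serious events and day-7 special-interest events can each be compared by arm. Only the comparison of all adverse events lacks a source.
- **That non-serious reports are discarded.** The symptom questionnaires may retain some of them. The text shows no provision for recording them as adverse events, which is less than showing that they are thrown away.
- **That the go decision would rest on truncated safety data.** The go rule uses only the one-sided p-value of the primary analysis.
- **That power for unrecorded events is zero.** This restates the premise and says nothing about how many events would go unrecorded.

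**Conclusion.** The inconsistency is real and should be corrected. The set of non-serious events to be recorded is narrower than both the set asked about and the set to be compared, and it is undefined. The consequence is an incomplete adverse event comparison and an incomplete DSMC review.

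The extent cannot be quantified from the documents, which give neither adverse event rates nor the special-interest list; it could be small or substantial. The conclusion rests on taking the section 3, item e, sentence as the operative rule for non-serious events. It is the only explicit one.

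**What to change.** 1. Amend section 3, item e, so that adverse effects reported on the existing contacts (days 1 to 7, 14 and 30) are recorded in both arms with date, seriousness and a special-interest flag, whether or not the study physician attributes them to study drug.
2. List the adverse events of special interest.
3. State how COVID-19 symptoms that count toward the efficacy endpoint are separated from adverse events. The overlap is concrete: shortness of breath is a COVID-19 symptom in this protocol, and exertional dyspnea is one of the late symptoms that participants are asked to report.
4. In the statistical section, compare all recorded adverse events, special-interest events and serious adverse events by arm, and give those tables to the DSMC.

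The cost is data entry and coding on contacts that already take place and already ask the question: at most 9 × 1600 = 14,400 scheduled contacts, with an entry only where something is reported. No visit or procedure is added. A cheaper alternative is to limit the planned comparison to serious events and a listed special-interest set. That would remove the contradiction, but would leave other non-serious events, and those reported after day 7, outside the safety record.
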